8.4.5. Time to Response

Time to response is defined as the time from randomization to the first confirmed CR or PR as assessed by IRC and Local Investigator's Review. Time to response will be analyzed for the RE $(3^{rd} line+)$ set via Cox proportional hazards modelling with a fixed effect term for treatment arm and stratified by stratification factors. The hazard ratio (balixafortide + eribulin vs eribulin monotherapy) will be estimated from the model along with the associated 95% CI and 2-sided p-value. The hazard ratio is interpreted, in the context of response, as the odds a patient will respond faster with the combination therapy as compared to eribulin monotherapy so a value > 1 shows the addition of balixafortide to be beneficial.

The data will also be displayed using Kaplan-Meier curves; median time to response and the 95% CIs will be estimated as described for PFS in Section 8.1.3.

Time to response, as assessed by local investigator's review will also be analyzed for the RE (3^{rd} line+) set as described for PFS in Section 8.1.3.

No censoring rule will apply since Time to Response will only be analyzed for patients achieving a confirmed response CR or PR.

This data will be presented in a listing for both IRC and local investigator's review.

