3.2.3. Other Secondary Efficacy Endpoints

Other secondary efficacy endpoints are considered supportive and will not be subject to overall Type I Error control. These endpoints are:

- PFS according to RECIST v1.1 guidelines, as assessed by the local Investigator's review.
- ORR (confirmed CR + confirmed PR) according to RECIST v1.1 guidelines, as assessed by the local Investigator's review.
- Clinical Benefit Rate (CBR) [proportion of patients with confirmed CR, confirmed PR, or stable disease (SD) ≥6 months] according to RECIST v1.1 guidelines, as assessed by (i) the IRC and (ii) the local Investigator's review.
- Disease control rate (DCR; number of patients with confirmed CR, confirmed PR, or SD) according to RECIST v1.1 guidelines, as assessed by (i) the IRC and (ii) the local Investigator's review.
- Time to response, as assessed by (i) the IRC and (ii) the local Investigator's review.
- Duration of response, as assessed by (i) the IRC and (ii) the local Investigator's review.

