4.3.6. Response Evaluable Set (3rd Line+)

The Response Evaluable (RE) set (3rd line+) will be used to evaluate disease response. The RE set (3rd line+) includes all randomized patients in the 3rd line+ population with measurable disease by RECIST v1.1 as determined by the Investigator at screening during the evaluation of breast cancer history. The co-primary endpoint analysis of ORR and other secondary endpoint analyses of CBR, duration of response, DCR and time of response will be conducted using the RE (3rd line+) set. Patients will be analyzed by the treatment arm to which they are randomized.

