8.4. Other Secondary Endpoints

Other secondary endpoints are PFS according to RECIST v1.1 guidelines, as assessed by the local Investigator's review, and ORR (confirmed CR + confirmed PR) according to RECIST v1.1 guidelines, as assessed by the local Investigator's review. Additionally CBR, DCR, time to response and duration of response will be analyzed. These analyses will be supportive in nature and, hence, will not be subject to Type I error control. Statistical tests will be 2-sided with a nominal Type I error rate of 0.05.

PFS and ORR as assessed by investigator, will be analyzed as described in Section 8.1.3 for the ITT (3rd line+) set. Date of Progression will be the date assessed by the investigator.

CBR and DCR will be analyzed in ITT (3rd line+) set and RE (3rd line+) set. Time to response and duration of response will be analyzed only in RE (3rd line+) set. These analyses will be performed for parameters defined from the best responses as assessed by (i) the IRC and (ii) the local Investigator's review.

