8.4.6. Duration of Response

Duration of response is defined as the time from first confirmed CR or PR until the earliest evidence of disease progression or death from any cause, as assessed by IRC review. The algorithm for calculation of Date of Progression and censoring rules will be the same as defined in the analysis for PFS, as described for PFS in Section 8.1.3.

Duration of response will be analyzed for the RE (3rd line+) set via Cox proportional hazards model with a fixed effect term for treatment arm and stratified by stratification factors. The hazard ratio (balixafortide + eribulin vs eribulin monotherapy) will be estimated from the model along with the associated 95% CI and 2-sided p-value. The data will also be displayed using Kaplan-Meier curves; median duration of response and the 95% CIs will be estimated as described for PFS in Section 8.1.3.

Since duration of response is assessed in responding patients only, the comparison is biased and could be misleading if the ORR differs moderately between the treatment arms. Hence, a supportive analysis will be performed based on the expected duration of response as per Ellis et al (2008) as this analysis includes all randomized patients, including those who did not respond, and so provides a valid comparison of the treatment arms. The expected duration of response is a product of the estimated fraction of patients with a response (ORR) and the mean duration of response in response in responding patients.

Duration of response, as assessed by local investigator's review, will also be analyzed for the RE $(3^{rd} line+)$ set as described for PFS in Section 8.1.3.

This data will be presented in a listing for both IRC and local investigator's review.

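### Time to response is compared between arms in confirmed responders only, with a hazard ratio above 1 read as benefit and no allowance for selection

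*SAP*

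**What the plan says.** SAP section 8.4.5 measures time to response from randomisation to the first confirmed CR or PR, once by IRC and once by investigator review. It names the Response Evaluable (3rd line+) set, as section 4.3.6 does: "duration of response, DCR and time of response will be conducted using the RE (3rd line+) set". That set is fixed by measurable disease at screening, so it contains patients who never respond.

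The method is a Cox model stratified by the randomisation factors, giving a hazard ratio with 95% CI and a 2-sided p-value. The ratio is to be interpreted "as the odds a patient will respond faster with the combination therapy", "so a value > 1 shows the addition of balixafortide to be beneficial". The section then narrows the analysis: "No censoring rule will apply since Time to Response will only be analyzed for patients achieving a confirmed response CR or PR".

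The next section, 8.4.6, treats duration of response differently. It warns: "Since duration of response is assessed in responding patients only, the comparison is biased and could be misleading if the ORR differs moderately". It adds an expected duration of response analysis on the ground that "this analysis includes all randomized patients, including those who did not respond, and so provides a valid comparison of the treatment arms".

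On status, section 3.2.3 states: "Other secondary efficacy endpoints are considered supportive and will not be subject to overall Type I Error control". Section 8.4 adds: "Statistical tests will be 2-sided with a nominal Type I error rate of 0.05". The protocol defines time to response (section 8.3.4) and lists it (12.2.7.4 and 12.3.7.4) but gives no model for it, so SAP 8.4.5 is the only specification.

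**The concern.** Response is itself an outcome of treatment. Once non-responders are removed and nobody is censored, the Cox model compares only the timing of response among those who responded. If the combination produces responses in patients who would not have responded to eribulin alone, the two responder groups are different kinds of patient. The ratio can then fall below 1 without any patient being slower, or rise above 1 because slow responders were lost.

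The SAP's wording refers to a patient, not a responder, and turns the ratio into a statement of benefit. (A hazard ratio is also not an odds.) An ORR difference, the condition under which 8.4.6 says a responder-only comparison misleads, is a co-primary hypothesis of this trial. At stake is a nominal p-value with a pre-specified benefit reading that could be quoted in a report and point the wrong way.

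**Working it through.** Section 8.4.5 states no figure to reproduce. The check has three parts.

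**1. Share of the set left out.** Background ORRs: eribulin 9–12% (protocol 2.2); combination 30% and 38% (protocol 2.5.1). These are literature and Phase 1 figures, not design assumptions. With equal arms, share left out = 1 − (control ORR + combination ORR)/2:

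- 12% and 38%: 1 − 0.25 = 75.0%
- 9% and 38%: 1 − 0.235 = 76.5%
- 12% and 30%: 1 − 0.21 = 79.0%
- 9% and 30%: 1 − 0.195 = 80.5%

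**2. Why the direction can reverse.** Assume control responders first respond at weeks 6/12/18/24/30 in proportions .50/.30/.12/.05/.03.

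- *ORR rises from 12% to 30%, the added 18 points responding later (.15/.30/.25/.20/.10).* Responding at week 6, all patients: control 0.12 × 0.50 = 6.0%; combination 6.0% + 0.18 × 0.15 = 8.7%. The combination is ahead. Among responders: control 50%; combination 8.7/30 = 29.0%. It looks slower.
- *ORR falls, with all week-6 responders kept, half of week-12 and none later.* Combination ORR = 0.12 × (0.50 + 0.15) = 7.8%. At week 6 both arms have 6.0% of all patients; by week 12 it is 9.6% against 7.8%. The combination is never ahead. Among responders at week 6: control 50%; combination 6.0/7.8 = 76.9%. It looks faster.

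**3. Simulation.** 2000 runs per case, 140 response-evaluable patients per arm (assumed), eight strata with assumed prevalences .7/.5/.8, geometric mean hazard ratio. The SAP names no tie method, so Breslow / Efron are both given. Moderately later timing is .30/.35/.20/.10/.05; earlier is .80/.15/.05/0/0.

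| Case | Responder-only HR | All-patient HR |
|---|---|---|
| 12% to 30%, added responders later | 0.66 / 0.59 | 2.7–2.9 |
| 12% to 30%, moderately later | 0.83 / 0.78 | 2.7–2.9 |
| 12% to 30%, same timing | 0.99 / 0.98 | 2.7–2.9 |
| 12% to 30%, earlier | 1.27 / 1.40 | 2.7–2.9 |
| 12% to 7.8%, slow responders lost | 1.61 / 1.89 | 0.64 |
| 20% (assumed) to 13%, slow responders lost | 1.59 / 1.94 | 0.63 |

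Nominal p<0.05 in favour of the combination occurs in 2% / 14% of trials for the fall from 12%, and in 10% / 41% for the fall from 20%. Adding the ±7 day scan window (Efron, 1500 runs) leaves the direction unchanged: later 0.57, moderately later 0.75, same 0.99, losses 2.08 and 2.09.

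A separate simulation with other assumptions (160 per arm, unstratified, Efron, 1000 runs, somewhat different timings) agrees. For 12% to 30% with the same timing, the responder-only ratio is 0.97 against 2.79 in all patients. With added responders later it is 0.54 against 2.69, nominally significant against the combination in 60% of runs. For 20% to 12% with faster responses it is 1.98 against 0.59, nominally significant in favour in 61%.

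**The case against.** The strongest reply is that the all-patient comparison already exists. Co-primary ORR compares confirmed response in the whole Response Evaluable set under controlled alpha, whereas duration of response has no such counterpart; that may be why only 8.4.6 adds one. If speed of response is the target, a ratio near 1 when timing is unchanged is the right answer. The case where harm reads as benefit rests on an invented loss pattern, the background ORRs point the other way, and a 20% control ORR lies outside the documents' 9–12%. Deleting the test also departs from protocol sections 12.2.7.4 and 12.3.7.4, which set a nominal 0.05 level; a caveat like that in 8.4.6 would be enough.

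Much of this stands as a limit on weight. ORR would show any fall in response. The simulated ratios support direction, not size. The share left out is not a measure of bias, and a descriptive responder summary omits the same patients.

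It does not rescue the rule. Even as a measure of speed, the comparison is confounded by who becomes a responder, and a stated benefit reading that can take the wrong sign is wrong as written. The protocol sets an alpha level but requires no model for this endpoint, and its sections 12.1 and 12.5 allow a non-confirmatory change if it is documented.

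**Conclusion.** The concern holds. SAP 8.4.5 makes a between-arm inference in a subset selected after randomisation and attaches a benefit reading that this subset cannot support; 8.4.6 recognises the same problem one section later. At the background ORRs, 75.0% to 80.5% of the Response Evaluable set would not enter the analysis. Under assumed timings, the responder-only ratio ranges from about 0.6 to 1.4 when ORR rises from 12% to 30%, and from about 1.6 to 1.9 when ORR falls. Those values depend on assumed response timing, strata and set size. The possibility of reversal does not depend on the exact values, as the week-6 arithmetic shows. The consequence is limited: this is a supportive endpoint outside Type I error control, and ORR, PFS and OS are untouched. It should be corrected but does not threaten the trial's main conclusions.

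**What to change.** For both the IRC and investigator versions, report time to response among responders descriptively by arm: the median with its within-arm 95% CI, which 8.4.5 already plans, and the range. Delete the between-arm hazard ratio, its CI and p-value, and the sentence reading a value above 1 as benefit. This is sufficient if speed among responders is the only interest.

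If a between-arm comparison is wanted, use cumulative incidence of response in all Response Evaluable (3rd line+) patients, with progression or death without response as competing events. State that it reflects response rate and speed together and largely restates ORR. Non-responders must stay in the denominator and not be censored at progression. With equal ORR (20%), equal timing and the SAP's design PFS medians of 3.9 and 5.8 months (exponential assumed, 2000 runs), censoring at progression gives a ratio of 0.88 where no response difference exists; keeping them in gives 1.00. The text should also name the test and say how it treats patients who withdraw, have no evaluable scan, or start new anti-cancer therapy before responding, since SAP 8.1.2 excludes their later scans.

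The cost is minor SAP wording and programming, an entry in SAP section 12 and a note in the study report. No new data are needed.

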8.4.6. Duration of Response

Duration of response is defined as the time from first confirmed CR or PR until the earliest evidence of disease progression or death from any cause, as assessed by IRC review. The algorithm for calculation of Date of Progression and censoring rules will be the same as defined in the analysis for PFS, as described for PFS in Section 8.1.3.

Duration of response will be analyzed for the RE (3rd line+) set via Cox proportional hazards model with a fixed effect term for treatment arm and stratified by stratification factors. The hazard ratio (balixafortide + eribulin vs eribulin monotherapy) will be estimated from the model along with the associated 95% CI and 2-sided p-value. The data will also be displayed using Kaplan-Meier curves; median duration of response and the 95% CIs will be estimated as described for PFS in Section 8.1.3.

Since duration of response is assessed in responding patients only, the comparison is biased and could be misleading if the ORR differs moderately between the treatment arms. Hence, a supportive analysis will be performed based on the expected duration of response as per Ellis et al (2008) as this analysis includes all randomized patients, including those who did not respond, and so provides a valid comparison of the treatment arms. The expected duration of response is a product of the estimated fraction of patients with a response (ORR) and the mean duration of response in response in responding patients.

Duration of response, as assessed by local investigator's review, will also be analyzed for the RE $(3^{rd} line+)$ set as described for PFS in Section 8.1.3.

This data will be presented in a listing for both IRC and local investigator's review.

8.5. Exploratory Efficacy Endpoints

Analysis of the other exploratory efficacy endpoints will not be subject to Type I error control. Statistical tests will be 2-sided with a nominal type I error rate of 0.05. Exploratory subgroup efficacy analyses of PFS, ORR and OS will be performed to qualitatively assess if the overall treatment effect is broadly consistent between clinically important subgroups.

The following subgroups will be analyzed for the ITT $(3^{rd} line+)$ set and for the RE $(3^{rd} line+)$ set as described below:

- Age category (<65yr vs ≥ 65 yr)
- Race (White, Black, Asian)
- Visceral disease at baseline (Yes versus No)
- Number of sites of disease involved (≤ 2 versus > 2)
- ECOG status at baseline (0 versus 1 versus 2)
- Prior treatment with cyclin-dependent kinase (CDK) 4/6 inhibitor (received a CDK 4/6 inhibitor vs not received a CDK 4/6 inhibitor) only for HR+ patients

- Prior capecitabine (Yes versus No)
- o Prior immune therapy (Yes versus No) only for TNBC patients
- Number of prior lines of therapy $(\leq 2, 3, \leq 4)$
- Receptor status [TNBC versus HR+]
- Estrogen receptor status (Positive versus Negative)
- Progesterone receptor status (Positive versus Negative)
- Metastasis in liver (Yes versus No)
- Metastasis in lung (Yes versus No)
- Time from initial diagnosis to randomization (<2 years versus ≥ 2 years)
- Region (USA, Europe, Asia and Latin America)

The following subgroups will be analyzed for the ITT (3^{rd} line+ Confirmed) set and for the RE (3^{rd} line+ Confirmed) set as described below:

- Receptor status [TNBC versus HR+]
- Prior treatment with cyclin-dependent kinase (CDK) 4/6 inhibitor (received a CDK 4/6 inhibitor vs not received a CDK 4/6 inhibitor) only for HR+ patients
- Visceral versus non-visceral disease

Subgroups analyses for PFS, as assessed by IRC, and OS will be achieved by use of a Cox proportional hazards model with fixed effect terms for treatment arm, the subgroup as a class variable and treatment arm by subgroup interaction. The p-value for the interaction will be used as guide to the statistical plausibility of a true difference in the treatment effect between levels of the subgroup; an interaction p-value <0.05 will be suggestive of a true difference in the treatment effect between levels of the subgroup. The hazard ratio (balixafortide + eribulin vs eribulin monotherapy) together with its 95% CI and 2-sided p-value will be presented for each level of the subgroup. The hazard ratios and associated 95% CI will be displayed in a forest plot along with the interaction p-value. Subgroup analyses above may not be performed if the sample size is too small to provide accurate estimate.

Subgroup analyses for ORR will be achieved via an exact logistic regression, including an interaction term for treatment arm by subgroup interaction. The odds ratio will be estimated from the model along with the associated 95% CI and 2-sided p-value, additionally the p-value for the interaction term will be presented on the summary table. Exact Clopper-Pearson 2-sided 95% confidence limits will be calculated for the proportion of patients with objective response in each arm.

Additional supplementary Bayesian subgroup analyses may be performed by the sponsor. To guard against random high and random low results associated with the analysis of multiple subgroups for which the trial was not powered and some of which may be small, these Bayesian subgroups analyses will be performed using R based on methodology as per Dixon and Simon (1991).

8.5.1. EORTC-QLQ-C30 QoL

The European Organization for Research and Treatment of Cancer (EORTC) QLQ-C30 (version 3.0) is a validated instrument to measure quality of life and assess symptoms and side effects of treatment and their impact on everyday life. Analysis of the EORTC-QLQ-C30 QoL data will be performed in the PRO (3rd line+) set.

The instrument is composed of 5 multi-item functional scales (physical, role, social, emotional and cognitive functioning), a global health status/QoL scale, 3 symptom scales (fatigue, nausea/vomiting and pain), and 6 single items (financial difficulties, appetite loss, diarrhea, constipation, insomnia and dyspnea). Most items are scaled 1 to 4 except the items contributing to the global health status/QoL, which are 7-point questions. Raw scores will be transformed using a linear transformation to standardize the results so that scores range from 0 to 100.

The calculation for scoring these scales is the same in all cases:

- 1. Calculate the average of the items that contribute to the scale; this is the raw score.
- 2. Use a linear transformation to standardize the raw score, so that scores range from 0 to 100; a higher score represents a higher (i.e. better) level of functioning, or a higher (i.e. worse) level of symptoms.

Calculations for raw score and linear transformation are as follows:

Let items $I_1, I_2, \dots I_k$ be included in a scale, where k is number of items in the scale, then:

$$Raw \ Score = RS = \frac{\sum_{j=1}^{k} I_j}{k}$$

To obtain the score for functional scales: $\left\{ \mathbf{I} = -\frac{RS-1}{range} \right\} \times 100$

To obtain the score for symptom scales/items and global health status/QoL: $= \left\{\frac{RS-1}{range}\right\} \times 100$

Range is the difference between the maximum possible value of *RS* and the minimum possible value.

The structure of the EORTC-QLQ-C30 questionnaire is presented in Scoring for QLQ-C30 version 3.0

Table 4 in Appendix 14.3).

At each assessment point, summary statistics of absolute scores and changes from baseline will be calculated by treatment arm for each scale for both the raw score and the linear transformed score. The baseline result will be the mean of the screening visit score and the score at last assessment prior to dosing. Summary tables and boxplots of the score by visit and treatment arm will be presented. The best and worst changes from baseline and associated time points will also be summarized using descriptive statistics. For functional scales and global health status, best changes from baseline are positive changes; while for symptom scales/items, best changes are negative changes.

The percentage of patients missing the entire questionnaire will be summarized and reason it is missing will be listed by treatment arm.

If more than 50% of questions are unanswered within a subscale at a particular timepoint, the value for the subscale will be set to missing. If less than 50% of questions are unanswered, the

sum of the scores for the answered questions will be taken and scaled up in relation to the number of questions in the scale answered or not.

The change from baseline for the linear transformed score will be compared between treatment arms for the PRO (3rd line+) set using mixed model repeated measures (MMRM) analysis with fixed effect terms for treatment arm, visit, treatment arm by visit interaction, the randomization stratification factors and also with baseline score as a covariate. Patient will be included as a random effect. The default estimation method of Restricted Maximum Likelihood (REML) and the Kenward-Roger (KR) option for degrees of freedom will be used. An unstructured covariance matrix will be used to model the within-patient error. If the fit of the unstructured covariance structure fails to converge, the following covariance structures will be tried in order until convergence is reached: Toeplitz with heterogeneity, autoregressive with heterogeneity, toeplitz, and autoregressive. A summary table will present number of subjects in each treatment group at each visit, LSMeans by treatment arm by visit, along with the difference in LSMeans, standard error, 95% CI and 2-sided p-value.

Patients will also be classified as improved, stable, or worsened. Minimal important difference (MID) thresholds, a threshold of 5 score points of the linear transformed score, will be used to categorize patients as improved, stable, or worsened. The first post-baseline assessment where either improved or worsened status is met will be used to assign patient status. The improved or worsened status has to be confirmed by the assessment at subsequent cycle.

The proportion of patients with each status will be calculated for each subscale based on patients who have at least two available change from baseline of the linear transformation scores in that scale. A proportional odds model will be used to test the difference in proportions of patient status between treatment arms for each scale; a fixed effect term for treatment will be included and the model will be stratified for randomization stratification factors. The odds ratio, 95% CI and 2-sided p-value will be extracted from the model and presented.

The individual questions and derived scales scores will be listed for the PRO (3rd line+) set.

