Results will be displayed as well as presented in a table, in terms of the overall odds ratio for balixafortide + eribulin vs eribulin monotherapy along with the associated 95% CI and 2-sided p-value. Odds ratios by visit will be displayed also.

EQ VAS

The EQ VAS records the patient's self-rated health visual analogue scale with endpoints labelled 'the best health you can imagine' and 'the worst health you can imagine'. The patient is asked 'mark an X on the scale to indicate how your health is TODAY' and then to 'write the number you marked on the scale in the box below'. There will be no programming checks for a discrepancy between where the patient has placed the X and the number they have written in the box, the number in the box is the only value available on the database and to be used for analysis.

EQ VAS scores will be analyzed across visits using an MMRM approach in the same manner as described in Section 8.5.1 for the EORTC-QLQ-C30.

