8.5.3. FACT-B

The FACT-B (version 4) is a self-administered questionnaire designed for patients suffering from breast cancer; FACT-B is a breast cancer subscale added to the Functional Assessment for Cancer Therapy -General (FACT-G). It consists of 37 questions grouped into 5 subscales being:

- Physical well-being (7 questions GP1 to GP7, min score=0, max score=28)
- Social/family well-being (7 questions GS1 to GS7, min score=0, max score=28)
- Emotional well-being (6 questions GE1 to GE6, min score=0, max score=24)
- Functional well-being (7 questions GF1 to GF7, min score=0, max score=28)
- Breast subscale (10 questions B1 to B9 and P2, min score=0, max score=40)

All questions are presented with answers on a five-point (0 to 4) Likert scale. As displayed in Appendix 14.4, subscale scores are calculated by first transforming all question scores within a subscale to have the same direction such that the higher the score, the better the QOL, and then summing the resulting scores. If more than 50% of questions are unanswered within a subscale at a particular timepoint, the value for the subscale will be set to missing. If less than 50% of questions are unanswered, the sum of the scores for the answered questions will be taken and scaled up in relation to the number of questions answered or not in the scale. The subscale scores will be combined as follows:

FACT-G total score: PWB score + SWB score + EWB score + FWB score

FACT-B total score: PWB score + SWB score + EWB score + FWB score + BCS score

No imputation will be done if any of the subscores is missing.

Analysis of the FACT-B data will be performed in the PRO set. The 5 subscale scores along with the FACT-G score and FACT-B total score will be summarized by treatment arm at each assessment point using mean, median, standard deviation, min, max and N.

Each of the subscale scores together with the FACT-G score, FACT-B total score will be analyzed over time using an MMRM approach in the same manner as described for the EORTC-QLQ-C30.

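### SAP 8.5.1 combines a random patient effect with an unstructured within-patient covariance, which leaves one covariance parameter unidentifiable and can trigger the step-down without need

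*SAP*

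**What the plan says.** SAP section 8.5.1 models change from baseline in the transformed QLQ-C30 score with fixed effects for arm, visit, arm by visit and the stratification factors, and baseline as a covariate. It then names two covariance components for the same model: "Patient will be included as a random effect" and "An unstructured covariance matrix will be used to model the within-patient error". On estimation it says: "The default estimation method of Restricted Maximum Likelihood (REML) and the Kenward-Roger (KR) option for degrees of freedom will be used".

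The step-down rule follows: "If the fit of the unstructured covariance structure fails to converge, the following covariance structures will be tried in order until convergence is reached". The list is "Toeplitz with heterogeneity, autoregressive with heterogeneity, toeplitz, and autoregressive". Non-convergence is the only trigger. Nothing is said about a fit that converges with a warning.

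The model is reused. Section 8.5.2 says "EQ VAS scores will be analyzed across visits using an MMRM approach in the same manner as described in Section 8.5.1 for the EORTC-QLQ-C30", and section 8.5.3 says that the FACT-B scores "will be analyzed over time using an MMRM approach in the same manner as described for the EORTC-QLQ-C30".

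Protocol section 12.2.7.5 asks only for a mixed model for repeated measures and mentions no random patient term. SAP section 12, which lists changes from the planned analyses, does not mention one either.

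**The concern.** A random patient intercept adds the same constant to every variance and covariance of a patient's repeated scores. An unstructured matrix can already take any symmetric positive-definite form, including one with that constant in it. The data therefore cannot separate the two, and the information matrix of the covariance parameters is singular.

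This has three practical consequences:

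- The redundant term can stop the optimiser from converging where the unstructured model alone would have fitted. The SAP's own rule then replaces the unstructured matrix with a more restrictive one.
- The Kenward-Roger adjustment uses the inverse of the information matrix that is singular here.
- If the software reports convergence with a Hessian or G-matrix warning, the SAP has no rule. The programmer of an open-label trial would have to decide after seeing the data.

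**Working it through.** The documents give no figure for this model, so there is none to reproduce. The check is algebraic, with a numerical confirmation.

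**Inputs.** The two covariance components, the fallback list and REML with Kenward-Roger come from SAP 8.5.1. The number of post-baseline visits, T, is not fixed: questionnaires are completed each cycle while on treatment. T = 3, 4, 6, 8 and 10 are therefore assumed.

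**Step 1: marginal covariance.** With patient variance τ² and within-patient matrix R, the covariance of one patient's scores is V = τ²J + R, where J is the T × T matrix of ones. V has T(T+1)/2 distinct elements.

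**Step 2: unstructured R.** R has T(T+1)/2 free parameters, so the model has T(T+1)/2 + 1. For any V, and any τ² small enough to keep R positive definite, R = V − τ²J gives the same V. The rank of the derivative of V's distinct elements with respect to the parameters was computed numerically:

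| T | Parameters with random effect | Distinct elements of V | Rank |
|---|---|---|---|
| 3 | 7 | 6 | 6 |
| 4 | 11 | 10 | 10 |
| 6 | 22 | 21 | 21 |
| 8 | 37 | 36 | 36 |
| 10 | 56 | 55 | 55 |

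There is one redundant parameter each time. Without the random effect, parameters equal distinct elements (10 and 10 at T = 4) and the model is full rank.

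**Step 3: likelihood.** Data were simulated for 320 patients in two equal arms with T = 4, complete visits, and visit and arm-by-visit effects only. V was held fixed while τ² was set to 0, 10, 20, 30 and 40 with R = V − τ²J. R stayed positive definite (smallest eigenvalue 61.009 falling to 60.277). The −2 REML log-likelihood was 7631.219204 in all five cases, with the same treatment estimates and standard errors. This must follow from step 2. It shows both that τ² carries no information and that treatment results do not depend on it.

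**Step 4: fallback structures plus a random patient effect, T = 4.**

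| Structure | Parameters with random effect | Rank |
|---|---|---|
| Heterogeneous Toeplitz | 2T = 8 | 8 |
| Heterogeneous autoregressive | T + 2 = 6 | 6 |
| Homogeneous Toeplitz | T + 1 = 5 | 4 |
| Autoregressive | 3 | 3 |

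Homogeneous Toeplitz fails because adding τ² to every band gives another homogeneous Toeplitz matrix. The pattern is the same at every T tried. For heterogeneous Toeplitz, full rank depends on standard deviations that differ between visits (values between 8 and 15 were used). With equal standard deviations the rank drops by one (8 parameters, rank 7, at T = 4), so the term may be only weakly identified there.

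**Step 5: outcomes affected.** QLQ-C30: 1 global + 5 functional + 3 symptom scales + 6 single items = 15. EQ VAS: 1. FACT-B: 5 subscales + FACT-G total + FACT-B total = 7. The sum is 15 + 1 + 7 = 23.

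**The case against.** The strongest defence is that the sentence is loose wording. The SAP calls the model an MMRM and places the covariance on within-patient error, and it never uses the term random intercept. If patient is meant only as the subject of the repeated measures, the model is standard. That is plausible, but the text names both components, and a programmer who follows it will fit both.

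A reader might also infer more than the documents support:

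- **That the fit must fail.** Software may set the patient variance to zero and converge. Step 3 shows that V, the treatment contrasts and their model-based standard errors are then unchanged. No fallback has been shown to occur, and no change in standard errors under one has been quantified.
- **That every patient-reported comparison is affected.** Improved, stable or worsened status is compared with a proportional odds model (SAP 8.5.1), and the five EQ-5D dimensions with GEE (SAP 8.5.2). Neither uses this model.
- **That the fallback is arbitrary.** The four structures and their order are pre-specified. Scales could end with different structures under any list triggered by non-convergence, and an unstructured matrix over many sparse late visits could fail on its own. Correcting the sentence removes only the failures that it causes.
- **That the random effect should go everywhere.** Under the autoregressive fallbacks it is identifiable and supplies a lasting between-patient correlation. Without it the correlation decays towards zero with visit spacing, which is more restrictive.

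**Conclusion.** The model as written is over-parameterised by exactly one covariance parameter under the unstructured structure, and again under homogeneous Toeplitz. This follows from the algebra at any number of visits. The possible harm is an avoidable step-down, a singular Hessian that undermines the Kenward-Roger calculation, or an unplanned decision about a warning. None of these is certain.

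The reach is 23 exploratory outcomes. SAP 8.5 places them outside Type I error control at a nominal 0.05, and the ORR, PFS and OS analyses are untouched. The point is minor and worth correcting because the correction is so cheap. It assumes that the sentence means a random patient intercept. If it means only the repeated-measures subject, the correction is editorial.

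**What to change.** In SAP 8.5.1, replace the random-effect sentence with: *Patient will be the subject of the repeated-measures covariance; no random patient effect will be fitted with the unstructured or homogeneous Toeplitz structures.* Add one sentence saying whether a random patient effect is kept under the heterogeneous Toeplitz and autoregressive fallbacks, where it is identifiable (for heterogeneous Toeplitz, provided that variances differ between visits). Sections 8.5.2 and 8.5.3 inherit the change by cross-reference.

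Keep REML and Kenward-Roger. A sandwich variance under the fallbacks is optional and not part of this fix. If one is added, the SAP should also state the degrees-of-freedom method that goes with it.

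The cost is two sentences of SAP text. Data collection and confirmatory testing do not change, and under the unstructured structure the marginal model and treatment estimates stay the same.
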